1.0 PROTOCOL SUMMARY AND/OR SCHEMA

Study Title: A phase I/II study of metformin in combination with cisplatin and radiation in head and neck squamous cell carcinoma.

Study Concept: The purpose of this study is to investigate the safety and efficacy of metformin when used in combination with standard of care cisplatin and external beam radiotherapy (EBRT) for patients with stage III/IV squamous cell carcinoma of the oropharynx, larynx, hypopharynx and oral cavity. Metformin is an anti-diabetic medication which has been widely utilized for nearly 2 decades, with a proven safety profile. Utilization of metformin during treatment of head and neck squamous cell carcinoma (HNSCC) has been shown to be associated with improved disease response, disease free survival and overall survival in retrospective studies. In combination with extensive pre-clinical studies, these data support the hypothesis that metformin can improve chemo-EBRT effectiveness in a prospective clinical trial. The proposed study is designed to determine whether metformin utilization in combination with standard of care cisplatin and EBRT demonstrates increased toxicity (phase I) and whether metformin utilization can improve the primary outcome of disease response (phase II) compared to historical controls treated with chemo-EBRT.

Study Design: This is a prospective study involving stage III/IV patients with squamous cell carcinoma of the oropharynx, larynx, hypopharynx and oral cavity. The phase I portion of the study will test 2 doses of metformin which are within the standard range used for management of diabetes mellitus. The goal of this phase I component is to determine whether metformin use is associated with increased systemic and locoregional treatment toxicity. The phase II portion will use the maximum tolerated dose (MTD) from the phase I to evaluate metformin efficacy in a prospective cohort of 20 patients using disease response as the primary outcome measure.

Number of Patients: 45

Primary Endpoint: The primary endpoint for the phase I component will be toxicity. The primary endpoint for the phase II component will be disease response ascertained via imaging following completion of treatment.

Secondary Endpoints: Secondary endpoints for the phase II component will include: progression free survival and overall survival.

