13.2 Sample Size/Accrual Rate

Phase I component considerations.

The study is designed to escalate the dose if the observed toxicity rate at the current dose is ≤ 0.2365 , and de-escalate the dose if the observed toxicity rate at the current dose is ≥ 0.3585 . If the observed toxicity rate is between 0.2365 and 0.3585, additional patients will be treated at the current dose. For cohorts of size 3, the decision boundaries are shown in table below. Two doses levels of Metformin (850 mg and 1500 mg) are evaluated, beginning with the lower dose.

DLT Regulation of Dose Escalation and De-Escalation									
Number of patients treated	3	6	9	12	15	18	21	24	27+1
Escalate*** if number of DLT <=	0	1	2	2	3	4	4	5	6
Treat additional 3 pts on current dose if number of DLT=	1	2	3	3,4	4,5	5,6	5,6,7	6,7,8	7,8,9
Deescalate* if number of DLT >=	2	3	4	5	6	7	8	9	10
Eliminate** if number of DLT >=	3	4	5	7	8	9	10	11	12

* At the lowest dose level, if the recommendation is to de-escalate AND the dose level has not been eliminated from consideration, 3 additional pts will be accrued at the same dose level; otherwise the trial will stop. Last cohort has 4 patients to reach the required sample size of 28.

** Eliminate dose level and all higher doses from further use.

*** At the time of the design change the study escalated to the highest dose and will continue enrolling additional patients at this dose unless de-escalation is recommended.

Phase II component considerations.

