A response rate $\geq 60\%$ would be considered effective for patients undergoing metformin plus standard of care, while a response rate $\leq 40\%$ is not considered as effective. The phase II portion of the trial would require at least 28 evaluable patients treated at the MTD. For the purposes of this study, a response will be defined as overall complete response (CR) or overall partial response (PR) (see Table in section 12.1.4.3). Stable disease or progressive disease will be defined as a non-response. The criterion for significance (alpha) has been set at 0.10. The test is 1-tailed, which means that an effect in one direction (improvement) is expected and will be interpreted. Calculation are based on the assumptions of uniform accrual over time. With the proposed sample size of 28 patients the study will have power of 80% to yield a statistically significant result. The treatment strategy (metformin plus standard of care) is considered effective if 17 or more responses are observed among the 28 patients.

Total study sample size.

This study will enroll at least 3 patients at each dose level and at least 28 patients at the MTD level. Participants will continue to be enrolled and monitored for toxicity according to the rules specified above until 28 efficacy evaluable participants have been enrolled to any single dose level. For the purposes of this analysis, a subject is considered evaluable for the primary endpoint after completing at least one dose of Metformin. It is expected that all dose levels will be safe and assuming that even the highest dose level has a DLT rate substantially lower than the target (i.e. $<10\%$), which is what we expect, we will have more than 99% chance of selecting the top dose level at the end of the trial. In this case the total number of patients enrolled would be 31 (3+28). Retrospective clinical studies have not demonstrated an increase in treatment toxicity for patients undergoing cisplatin for HNSCC while taking metformin. It is anticipated that 1-2 patients per month

will be accrued to the study. Depending on the toxicity, this will allow for completion of study within 33-39 months of study initiation.

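### Section 1.0 gives phase II 20 patients where section 13.2 requires 28, and its total of 45 is neither derived nor reconciled with the conditional 31

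*Combined protocol and SAP*

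**What the plan says.** Section 1.0 (protocol summary) gives two figures. The overall size is "Number of Patients: 45", and the phase II part is meant "to evaluate metformin efficacy in a prospective cohort of 20 patients using disease response as the primary outcome measure".

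Section 13.2 gives different ones:

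- For efficacy: "The phase II portion of the trial would require at least 28 evaluable patients treated at the MTD".
- The footnote to the dose-decision table agrees: "Last cohort has 4 patients to reach the required sample size of 28".
- For the whole study it sets minimums: "This study will enroll at least 3 patients at each dose level and at least 28 patients at the MTD level". Accrual runs until 28 efficacy-evaluable participants are on any single dose level.
- For the case where the top dose is selected: "In this case the total number of patients enrolled would be 31 (3+28", that is, 3 at the lower level and 28 at the higher.

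The phase II test in 13.2 sets a 40% response rate against 60%, one-sided alpha 0.10 and 80% power with 28 patients. Success is 17 or more responses among the 28.

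Two places bear on the 3+28 split. A footnote in 13.2 says that the study had escalated to the highest dose when the design was changed and keeps enrolling there. Section 6.1 says that escalation to Dose level 2 is forgone and that phase II proceeds at Dose level 1.

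**The concern.** The document gives two sizes for the one cohort that carries the primary efficacy test, and no section says which prevails. The size fixes when efficacy accrual ends and what power the test has. A team working from the synopsis would plan for 8 fewer patients than the statistical section requires.

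The planned total also has a use in oversight. Section 16.0 has the Data Review Committee look at accrual together with the expected number of patients. With 45 in one section, a conditional 31 in another and no derivation of 45, that expected number is not defined.

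**Working it through.** **Inputs, all from section 13.2:** null response rate 0.40, alternative 0.60, one-sided alpha 0.10, power 0.80, N = 28, success at 17 or more responses. From section 1.0: phase II N = 20, total 45.

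**Step 1: reproduce the 28.** By the normal approximation for one proportion, with p(1−p) = 0.24 under both rates:

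n = (z0.90 + z0.80)² × 0.24 / (0.60 − 0.40)² = (1.2816 + 0.8416)² × 0.24 / 0.04 = 27.05, rounded up to 28.

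The arcsine approximation gives 27.8, again 28. Power at 28 is 81.0% (normal) or 80.2% (arcsine). So 28 follows from the stated inputs.

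**Step 2: the same test with 20 patients.** The approximations give 70.7% (normal) and 69.8% (arcsine). For the exact binomial, alpha = P(X ≥ r) at p = 0.40 and power = P(X ≥ r) at p = 0.60:

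| n | Success if responses ≥ | Exact alpha | Exact power |
|---|---|---|---|
| 20 | 11 | 0.1275 | 75.5% |
| 20 | 12 | 0.0565 | 59.6% |

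Eleven exceeds alpha 0.10 and still falls short of 80%. Twelve is the lowest cutoff within alpha, and it is 80 − 59.6 = 20.4 points short. No 20-patient rule meets the stated alpha and power together.

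**Step 3: the 28-patient rule as written.**

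| n | Success if responses ≥ | Exact alpha | Exact power |
|---|---|---|---|
| 28 | 15 | 0.1025 | 81.3% |
| 28 | 16 | 0.0499 | 69.5% |
| 28 | 17 (stated) | 0.0215 | 55.1% |

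The stated cutoff has slightly less power than 12 of 20 (55.1% against 59.6%), at a smaller alpha. This is a separate defect, but it means that putting 28 in the synopsis does not by itself give 80% power. The smallest single-stage size that meets both limits exactly is 30, with 16 or more responses (alpha 0.0971, power 82.5%).

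**Step 4: the totals.** 3 + 28 = 31 is correct as a sum. It describes a trial with 3 patients at Dose level 1 and 28 at Dose level 2. That fits the footnote in 13.2 but not section 6.1. If phase II is at Dose level 1, the 28 belong to that level, and the total becomes 28 plus however many patients were treated at another level, a number the documents do not give. No section derives 45, calls it a maximum, or states an allowance for non-evaluable patients.

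**The case against.** The best defence is that section 13 is the operative statistical text, that it states 28 consistently, and that the synopsis figures may be left over from the earlier 3+3 and Simon design that section 13.1 mentions. That may be the history. It shows which figure was probably intended, but it does not remove the other from current text.

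One could also read 28 as 20 phase II patients plus 8 phase I patients at the MTD. No section says so. Section 4.0 applies the HPV and smoking criterion to phase II only, so such pooling would have to be stated.

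The defence is right on three stronger readings that a reader might infer:

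- **That 45 and 31 contradict each other.** The documents do not show this. The 31 applies only if the top dose is selected, 13.2 otherwise gives minimums, and the total under the dose rules varies. The 45 could be a ceiling. The fair charge is that it is unexplained.
- **That the 17-response cutoff would be applied to 20 patients**, with about 1.6% power. Section 13.2 ties the cutoff to the 28 patients, so nothing in the plan leads there.
- **That 45 patients could be enrolled with no decision rule.** Section 13.2 stops at 28 evaluable on a single dose level and gives a rule for those 28. A total of 45 across levels would not make 45 the efficacy denominator.

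On the dose split, section 6.1 notes that Dose level 2 text was kept for documentation. Even if that note reaches section 13.2, the 3+28 sum would then describe a course the trial no longer follows.

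**Conclusion.** The point holds for the phase II size: 20 in section 1.0 contradicts at least 28 in section 13.2. With 20 patients, exact power within one-sided alpha 0.10 is at most 59.6%, against the stated 80%. This rests on the response rates and alpha in 13.2 and on a single-stage exact test, as current text describes no interim efficacy look.

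For the total, the finding is weaker: 45 has no derivation and is not reconciled with the conditional 31. The 3+28 behind that 31 depends on a conflict between 6.1 and 13.2 that must be resolved first; which dose course is correct is for the sponsor to state.

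This is an internal inconsistency in a figure the trial relies on. The intended 28 can be inferred, so it should be corrected, but it does not by itself invalidate the design.

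**What to change.** 1. In section 1.0, replace the 20-patient phase II cohort with the 28 evaluable patients of section 13.2.
2. Reconcile section 6.1 (Dose level 2 forgone) with the footnote in 13.2 (study already at the highest dose). Then state one total in both 1.0 and 13.2, labelled as expected or maximum, with its derivation.
3. Show any allowance for non-evaluable patients in that derivation. It needs one definition of evaluable: section 6.1 asks for at least 70% of the metformin dose due during radiation, while 13.2 asks for one dose.
4. Settle N and the cutoff together, because 17 of 28 does not give the stated alpha and power. If the remedy changes N, for example to the exact single-stage 30, carry the new number into section 1.0 as well.

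If 28 is kept, the first step is a wording change and adds no patients to what 13.2 already requires. The total needs edits to 1.0 and 13.2, and to 6.1 if that is the text that gives way. Moving to 30 would add 2 evaluable patients.

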2.0 OBJECTIVES

2.1 Primary Objectives

The primary objective for the phase I component is to define the maximum tolerated dose (MTD) of metformin and to document the safety of this compound when used in combination with cisplatin and external beam radiotherapy (EBRT).

The primary objective for the phase II component is to measure the effect of metformin in combination with standard of care cisplatin and EBRT on disease response when compared to historical controls treated with standard of care cisplatin and EBRT.

2.2 Secondary Objectives

Secondary endpoints for the phase II component will include: progression free survival and overall survival.

3.0 BACKGROUND AND RATIONALE

3.1 Study Disease

Every year, over 500,000 patients are diagnosed with a squamous cell carcinoma of the oral cavity, oropharynx, larynx and hypopharynx of which over 100,000 will be diagnosed in the US alone.¹ Non-operative management of these cancers has become the preferred approach over the last decade (NCCN guidelines). Advances in combinations of systemic therapy (cisplatin) and external beam radiotherapy (EBRT) technology has succeeded in decreasing treatment related toxicity, but survival rates for patients with advanced, stage III-IV disease remain low. This is particularly true for patients with stage III-IV SCC of the oropharynx, larynx, hypopharynx and oral cavity which do not exhibit evidence of infection with the human papilloma virus (HPV).²⁻⁶ In contrast to HPV+ patients, HPV- patients continue to demonstrate low rates of disease control, disease free and overall survival. The overall goal of this study is to test the potential of metformin as an adjunct to standard of care non-operative management consisting of cisplatin and EBRT for patients with stage III/IV, HPV- SCC.

3.2 Agent/Drug Information

Metformin is a well-tolerated anti-hyperglycemic agent used by more than 120 million patients worldwide. Metformin has a demonstrated safety and efficacy profile in preventing diabetes and improving metabolic and hormonal parameters in non-diabetic patients with insulin resistance and polycystic ovary syndrome (PCOS).⁷ Metformin safety has also been demonstrated in patients with non-alcoholic fatty liver disease.⁸

3.2.1 Antitumor Activity

Metformin has been shown by multiple investigators (including the principal investigator) to possess antitumor activity in preclinical models of squamous cell

carcinoma of the oral cavity, lung carcinoma, prostate carcinoma and breast carcinoma.⁹⁻¹¹ Retrospective data series have also shown improved clinical outcomes in patients taking metformin during treatment with standard of care regimens.¹¹⁻¹⁴

3.2.2 Summary of Preclinical Studies

Over the last few years, multiple investigators have demonstrated an important relationship between radiation effects on tumor cells and tumor cell metabolism. This relationship is dictated to a large degree by the master metabolic regulators AMPK and mTOR.^{9, 10, 15-17} We and others have shown that AMPK acts not only as a metabolic but also a genomic stress sensor that mediates cell cycle checkpoints and activates signaling events leading to radio-sensitization and cell death.^{15, 16, 18} Metformin can exhibit profound effects on cellular metabolism, activate AMPK signaling and radiosensitize tumors in a variety of pre-clinical models.^{9, 10, 19} In addition, metformin can potentiate the effectiveness of conventional chemotherapeutic agents in the pre-clinical setting.^{20, 21} Importantly, metformin effects occur at doses that can be safely achieved in the serum of patients treated with standard oral doses of metformin.²²

3.2.3 Summary of Clinical Studies

Clinical evidence to date indicates that utilization of metformin during cancer treatment can improve clinical outcomes in tumors of the upper aero-digestive tract.^{10, 13, 23} To date, we have not detected evidence of increased treatment (chemotherapy + EBRT) toxicity in diabetic patients treated with metformin who received standard of care chemotherapy and EBRT.

3.3 Rationale for Development

Patients with stage III/IV HPV- SCC of the oral cavity, oropharynx, larynx and hypopharynx continue to demonstrate low rates of disease response and survival when treated with current standard of care chemotherapy and EBRT.^{2-4, 6} There is a need to identify novel agents which can be added to standard of care regimens in order to improve disease outcomes. Because the toxicity of conventional chemotherapy and radiation is often additive and can prevent treatment escalation, there is a need to identify agents whose toxicity profile does not overlap with that of conventional treatment regimens. Metformin has an excellent safety record to date despite nearly 2 decades of widespread utilization in the United States. Phase I and II studies have demonstrated safe metformin use in non-diabetic patients.²⁴⁻²⁷ Metformin does not cause hypoglycemia, has favorable metabolic effects on insulin resistance and obesity, and is not associated with lactic acidosis at standard therapeutic doses.^{28,29}

Although metformin is currently being investigated in multiple other disease sites, there are no active clinical trials investigating the efficacy of metformin in combination with cisplatin and EBRT in the treatment of SCC of the oral cavity, oropharynx, larynx and hypopharynx. A single phase I trial is currently underway at the University of Cincinnati using dose of metformin higher than those proposed here and higher than those utilized in standard treatment of diabetes

mellitus. A phase I component was included in the current trial in order to evaluate any potential increase in toxicity associated with the combination of metformin, cisplatin and EBRT. The phase II component of this trial is the first of its kind in this disease site, and will provide the first prospective data regarding the potential efficacy of metformin in improving clinical outcomes for patients with stage III/IV HPV- SCC of the oral cavity, oropharynx, hypopharynx and larynx.

3.4 Correlative Studies Background

The preclinical data summarized above suggests that metformin can improve the cytotoxicity of chemotherapy and radiation, in part through perturbation of tumor metabolic pathways.^{9, 10} We and others have shown that tumor cells which exhibit a less flexible metabolic phenotype are more susceptible to metformin effects.^{9, 10} As a result, it is important to evaluate the metabolic phenotype of the patient tumors included in this study, in order to identify potential metabolic signatures of those tumors which are most responsive to metformin. To that end, tumors from patients enrolled in this study will be subjected to a multi-platform (mass spectroscopy / liquid chromatography) metabolomics analysis.³⁰

Our preliminary studies indicate that metformin preferentially radiosensitizes tumor cells which express mutant TP53.^{9, 10} Since metformin effectiveness can be impacted by the presence or absence of this and potentially other oncogenic events, we will evaluate the mutational landscape of tumors evaluated in this study using targeted sequencing.

Metformin has recently been shown to regulate the immune response associated with tumor development by regulating T cell survival and apoptosis.³¹ Since the immune response can play an important role in regulation of tumor growth and treatment response, we will perform correlative studies for the following: 1) changes in circulating immune cells (i.e. effector T cells, myeloid derived suppressor cells, regulatory T cell) levels in patients before and after treatment completion; 2) changes of other cellular and humoral immune response related parameters before and after treatment completion. The correlative studies performed as part of this clinical trial will not impact treatment selection and will not be available to the treatment team. All correlative studies will be performed following completion of the prospective therapeutic trial.

4.0 PATIENT ELIGIBILITY: PATIENT INITIALS (FML):_____

_____ a. Diagnosis: Patients must have histologically or cytologically confirmed squamous cell carcinoma (SCC) of the oral cavity, oropharynx, hypopharynx or larynx. Patients eligible for inclusion must have stage III-IV SCC of the above sites based on current AJCC clinical and imaging based staging (see **Appendix A** for staging criteria). For the phase II component, patients should present with: 1) HPV- SCC or 2) HPV+ SCC and a concomitant ≥ 10 pack-year smoking history documented in the clinical record; HPV status will be ascertained using the currently utilized clinical standard of p16 overexpression via immunohistochemistry for all patients. Immunohistochemistry to determine p16 overexpression is only a requirement for oropharyngeal disease.^{2,4}

_____ b. Disease Status: Patients must have active, measurable disease to be included in the study.

_____ c. Prior Therapy: Patients must have fully recovered (ECOG 0-1) from the acute toxic effects of all prior chemotherapy, immunotherapy, or radiotherapy prior to entering this study.

_____ d. Myelosuppressive chemotherapy: Must not have received within 4 weeks of registration onto this study (6 weeks if prior nitrosourea).

_____ e. Hematopoietic growth factors: Patients must be at least 7 days since the completion of therapy with a growth factor prior to registration.

_____ f. Biologic (anti-neoplastic agent): Patients must be at least 7 days since the completion of therapy prior to registration.

_____ g. Monoclonal Antibody: At least 6 weeks must have elapsed since prior therapy that includes a monoclonal antibody prior to registration.

_____ h. XRT: Prior to registration, patients must be ≥ 14 days for local palliative XRT (small port); ≥ 90 days must have elapsed if prior TBI, craniospinal XRT or if $\geq 50\%$ radiation of pelvis; ≥ 45 days must have elapsed if other substantial bone marrow radiation.

_____ i. Stem Cell Transplant or Rescue: No evidence of active graft vs. host disease and ≥ 2 months must have elapsed since transplant prior to registration.

_____ j. Age: Patients must be ≥ 18 years of age.

_____ k. Performance Status: ECOG performance status less than or equal to 3.

_____ l. Organ Function: Patients must have normal organ and marrow function as defined below, within 14 days of registration:

i. leukocytes	$\geq 3,000/\text{mcL}$
ii. absolute neutrophil count	$\geq 1,500/\text{mcL}$
iii. platelets	$\geq 100,000/\text{mcL}$
iv. total bilirubin	within normal institutional limits
v. AST(SGOT)	$\leq 2.5X$ institutional upper limit of normal
vi. ALT / (SGPT)	$\leq 2.5X$ institutional upper limit of normal
vii. creatinine $< 1.5\text{mg/dL}$ OR creatinine clearance $\geq 60 \text{ mL/min}/1.73 \text{ m}^2$ for patients with creatinine levels $>$ institutional normal	

- _____ m. Patients must be candidates for standard of care treatment consisting of chemotherapy (cisplatin) and radiation.
- _____ n. Willingness to Use Contraception: The effects of metformin on the developing human fetus at the recommended therapeutic dose are unknown. For this reason, women of child-bearing potential and men must agree to use adequate contraception (hormonal or barrier method of birth control; abstinence), 30 days prior to study drug initiation and 30days post completion of study drug administration. Should a woman become pregnant or suspect she is pregnant while participating in this study, she should inform her treating physician immediately.
- _____ o. Informed Consent: Patients must have the ability to understand and the willingness to sign a written informed consent document.
- _____ p. Patients may not be receiving any other investigational agents.
- _____ q. Brain metastases: Patients may not have diagnosed brain metastases.
- _____ r. Prior Allergies: Patients may not have a history of allergic reactions attributed to compounds of similar chemical or biologic composition to metformin.
- _____ s. Patients must not have a diagnosis of diabetes mellitus (DM) or be receiving active treatment for DM. If patient does not have known DM diagnosis, the patient must have either fasting glucose or hemoglobin A1C test within 30 days of registration. Patient is not eligible if glucose level \geq 126mg/dl or hemoglobin A1c \geq 6.0%. (Either test is sufficient for eligibility; both tests are not needed.)
- _____ t. Patients may not have an uncontrolled intercurrent illness including, but not limited to, ongoing or active infection, symptomatic congestive heart failure, unstable angina pectoris, cardiac arrhythmia, or psychiatric illness/social situations that would limit compliance with study requirements.
- _____ x. Patients may not be pregnant or breastfeeding.
- _____ y Patients may not have diagnosed HIV.
- _____ z. Patients may not be taking metformin for a reason other than study participation.

_____aa. Patients may not have been treated for another SCC of the oral cavity, oropharynx, hypopharynx or larynx in the past.

Both men and women and members of all races and ethnic groups are eligible for this trial. Approximately 40% of the patient population in Harris County is Hispanic and many are primarily Spanish speaking, thus we will provide a fully translated and IRB approved Spanish consent to these subjects.

